Cover Page

Official title of the study: Coil Hysteroscopic Tubal Occlusion,
the Treatment of Hydrosalpinx Before IVF-ET

Date: 12/01/2015

Study protocol

The problem to be investigated

Project title: Coil Hysteroscopic Tubal Occlusion, the Treatment of Hydrosalpinx Before IVF-ET

Research problem: This will be an investigation to evaluate the success rate of proximal tubal occlusion with coil devices in women with hydrosalpinx and to observe the pregnancy rate with IVF-ET.

Background: Many studies have proposed that hydrosalpinx fluid may decrease the pregnancy rate following IVF-ET (Zeyneloglu HB, 1998; Strandell A, 1999; Nackley AC, 1998).

During nearly two decades, researchers have find many treatments to improve the outcomes of IVF-ET with hydrosalpinx, such as fluid extraction, salpingectomy, proximal tubal occlusion with Essure device (HTO-E) and other devices (D'Arpe S, 2015; Lorente Gonzalez J, 2016;). However, extraction cannot prevent the refluxing of fluid which may directly poison the embryos while salpingectomy may decrease the ovarian response. Laparoscopic salpingectomy may increase the risk for patients who have had a history of severe pelvic adhesions. Besides, proximal tubal occlusion with Essure have been demonstrated to be companied by some severe

complications (Walter JR, 2017). Therefore, another safer device should be investigated. Fibered platinum coils have been used in aneurysm and endovascular therapy more than a decade ago (Tsai CW, 1996). However, with wide usage, the complication was few (Syha R, 2016).

The aims: The aim of our study was to evaluate the successful and complication rate after occlusion with fibered platinum coils, and to observe the pregnancy rate following IVF-ET.

(v) The hypothesis: Hysteroscopic occlusion will be an alternative to the treatment of hydrosalpinx before IVF-ET.

2. Methods of investigation:

Subjects: 80 females between 20-45 years old with unilateral or bilateral hydrosalpinx as confirmed by HSG.

Inclusion criteria:

1. Have unilateral or bilateral hydrosalpinx as evidenced by HSG.
2. Laparoscopic surgery was considered to be contraindicated because of suspected extensive pelvic adhesions.
3. Patients are willing to undergo a hysterosalpingogram (HSG) 3 months after tubal occlusion.
4. Patients are willing to participate in this clinical study.
5. Patients are able to comprehend and give informed consent

for participation in this study.

6. Have read, understood and signed an informed consent form.

Exclusion Criteria:

Active or recent upper or lower pelvic infection

Known hypersensitivity to nickel as confirmed by skin test

Known allergy to contrast media pregnancy or suspected pregnancy

Poor general or gynecologic health

Inability or refusal to provide informed consent

Design: subjects who meet the inclusion and exclusion criteria will be eligible, all the eligible subjects will be interviewed and the purpose of the trial will be outlined. Epidemiologic data will also be collected.

Experimental procedure: hysteroscopic tubal occlusion will be performed in the 3-7days after the menses. In the third day after the surgery, a vaginal ultrasound will be performed to confirm the position of coil. 3 months later, HSG will be taken out to confirm the occlusion of tubes. After the treatment, IVF-ET will be applied and then the patients' pregnancy rate will be assessed in the following-up.

Cover Page

Official title of the study: Coil Hysteroscopic Tubal Occlusion,
the Treatment of Hydrosalpinx Before IVF-ET

Date: 12/01/2015

Statistical Analysis Plan

1. Measurements used: Successful placement of coils will be judged by the correct placement that confirmed by vaginal ultrasound examination. Implantation rate, first-trimester spontaneous miscarriage rate and on-going pregnancy rate will also be calculated.
2. Sample size calculation: As a single-arm trial, 80 females will be recruited in our study.
3. Statistical methods: Data analysis was performed with SPSS version 22.0 (SPSS, Inc., Chicago, IL, USA), using two-sided test, and a p value < 0.05 was considered statistically significant. The participants who received insertion of fibered coils were followed up and the outcomes were recorded. Chi-square test will be applied to evaluate the basic data of the participants including age and IVF-ET cycles. Ratio was applied in the outcomes of miscarriage rate and pregnancy rate.

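### The SAP plans a coil-placement rate on ultrasound but no rate of tubal occlusion on the 3-month HSG, although occlusion is the protocol's first research question

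*SAP*

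**What the plan says.** **Protocol, Research problem.** The study is to "evaluate the success rate of proximal tubal occlusion with coil devices in women with hydrosalpinx" and to observe pregnancy after IVF-ET.

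**Protocol, The aims.** The aims are to "evaluate the successful and complication rate after occlusion with fibered platinum coils", again with pregnancy as a further observation.

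**Protocol section 2, Experimental procedure.** Two checks are scheduled, each with its own purpose. On the third day after surgery, "a vaginal ultrasound will be performed to confirm the position of coil". Then, "3 months later, HSG will be taken out to confirm the occlusion of tubes".

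**Protocol section 2, Inclusion criteria.** Entry depends on agreeing to the later check: "Patients are willing to undergo a hysterosalpingogram (HSG) 3 months after tubal occlusion".

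**SAP section 1.** The one item described as successful is placement: "Successful placement of coils will be judged by the correct placement that confirmed by vaginal ultrasound examination". The section then lists implantation, early miscarriage and ongoing pregnancy. HSG is not mentioned anywhere in the SAP, and occlusion appears only in its title. Complications are not listed.

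**SAP section 3.** Women in whom coils were inserted are described as followed up, with outcomes recorded. Nothing is said about women in whom insertion failed.

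**The concern.** The protocol treats coil position and tubal occlusion as two findings, made by two examinations about three months apart. The SAP plans an analysis of the first only. The study's first question therefore has no planned estimate, even though the examination that would answer it is already scheduled.

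A placement rate and an occlusion rate differ whenever a correctly placed coil leaves a tube open, or a tube is closed although the coil was not judged correctly placed. In a single-arm study these proportions are the main evidence on the procedure. An HSG proportion can always be calculated later. However, the choice of headline, the unit (woman or tube, since bilateral disease is eligible), the denominator and the handling of missing HSGs would then be made with the results in view.

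The complication rate has the same problem: it is named in the aims and absent from the SAP measurements.

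**Working it through.** **1. Text comparison**

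| Question in the protocol | Check named in the protocol | Measure in the SAP |
|---|---|---|
| Coil position | Vaginal ultrasound, third day | Successful placement on ultrasound |
| Tubal occlusion | HSG, 3 months | None |
| Complications | None named | None |
| Pregnancy after IVF-ET | Follow-up | Implantation, miscarriage and ongoing pregnancy rates |

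The second and third rows are the gap. The IVF outcomes do not fill the second row, because none of them shows whether a tube is closed.

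**2. Figures in the plan**

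The only figure that bears on this point is the sample size of 80. The SAP gives no expected rate, reference rate, precision or dropout behind it, so there is nothing to reproduce.

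**3. How far the two rates could differ (illustration; every rate is assumed)**

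Unit: women, with 80 attempted. Let *a* be the number correctly placed but not confirmed occluded on HSG, and *b* the number not correctly placed but confirmed occluded. Then

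placement rate − HSG occlusion rate = (*a* − *b*)/80.

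Take 76 of 80 correctly placed: 95.0% (exact 95% CI 87.7 to 98.6).

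With *b* = 0:

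| Occluded among the 76 | HSG rate | Exact 95% CI | Difference |
|---|---|---|---|
| 76 (100%) | 76/80 = 95.0% | 87.7 to 98.6 | 0 |
| 72 (about 95%) | 72/80 = 90.0% | 81.2 to 95.6 | 5.0 points |
| 68 (about 90%) | 68/80 = 85.0% | 75.3 to 92.0 | 10.0 points |
| 61 (about 80%) | 61/80 = 76.25% | 65.4 to 85.1 | 18.75 points |

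With 72 of the 76 occluded (*a* = 4) and *b* varied over the other four women:

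- *b* = 0: 72/80 = 90.0%, difference (4 − 0)/80 = 5.0 points
- *b* = 2: 74/80 = 92.5%, difference (4 − 2)/80 = 2.5 points
- *b* = 4: 76/80 = 95.0%, difference (4 − 4)/80 = 0 points

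If *b* exceeds *a*, the HSG rate is the higher of the two. For example, *a* = 0 and *b* = 4 gives −5.0 points.

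**4. Why the added outcome needs its own denominator (illustration)**

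Suppose 4 insertions fail with no HSG, 4 more women have no HSG, and 68 of the remaining 72 are confirmed occluded:

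- all attempted: 68/80 = 85.0% (75.3 to 92.0)
- inserted only: 68/76 = 89.5% (80.3 to 95.3)
- HSG done: 68/72 = 94.4% (86.4 to 98.5)

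This shows what is left open if the outcome is added without a denominator. It does not measure the omission itself, since unstated denominators are a general weakness of this SAP.

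**The case against.** **The SAP omits; it does not contradict.** SAP section 1 defines successful placement, not successful occlusion, and that matches the role the protocol gives to ultrasound. This stands. A reader might infer that the SAP redefines occlusion success as placement, but the text does not say so.

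**A procedural reading is possible.** Success is never formally defined, no passage calls the HSG result an endpoint, and occlusion is also the name of the operation, as in "hysteroscopic tubal occlusion will be performed in the 3-7days after the menses". On that reading, correct placement could count as success. It fits poorly with a separate, later examination whose stated purpose is to confirm occlusion, and with an entry criterion that secures it. If the sponsor did mean this, the SAP should say so.

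**The HSG data will be collected anyway, and no test depends on them.** This is true. There is no success threshold, reference rate or designated primary endpoint, so no planned test or sample size becomes wrong. The harm is a missing planned estimate and freedom to choose the headline afterwards.

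**Two stronger readings are not supported.** A reader might infer that SAP section 3 restricts analysis to women with an insertion. It describes their follow-up and is silent on the others; it does not exclude them. A reader might also take reflux as the protocol's central rationale for occlusion. The Background raises it as a drawback of another treatment ("extraction cannot prevent the refluxing of fluid which may directly poison the embryos") and introduces the coil as a safer device after describing complications of an existing one.

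**The sizes are invented.** They are assumed throughout. The largest difference shown simply reflects the 80% occlusion input, and zero is equally compatible with the documents.

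**Conclusion.** The point holds as an omission from the SAP. The protocol asks first about occlusion and names the 3-month HSG as its check. The SAP measures placement and IVF outcomes only, so following it gives no planned occlusion rate and no complication rate. This is more than missing detail, because the study's first question is left without an outcome in the analysis plan.

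The numerical consequence is unknown. On the assumed inputs above, the difference between the two rates runs from 18.75 points through zero to a small advantage for HSG. The documents do not allow a choice within that range. The conclusion rests on the text comparison and on reading occlusion in the Research problem as a closed tube, which the protocol's own split between position and occlusion supports.

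**What to change.** **In SAP section 1:**

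- Add HSG-confirmed occlusion at 3 months as the occlusion success outcome, per woman: success means that every tube in which placement was attempted is shown occluded on HSG. Judge it on the HSG alone, not on ultrasound placement, and add one line on how occlusion is read.
- Use all women with attempted placement as the denominator. A woman with no HSG for any reason, including a failed insertion, counts as not confirmed.
- Report the proportion with an exact 95% CI, and a supportive analysis among women who had an HSG.
- Keep ultrasound placement as a separately named technical outcome, cross-tabulated with the HSG result.
- Add the complication rate named in the aims, among all women with attempted placement.

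**In SAP section 3:** state that women with a failed insertion stay in the occlusion denominator.

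**Cost.** This is SAP wording, with a one-line reading definition and a short list of complications. The HSG is already scheduled, and a woman without one is simply scored as not confirmed, so no visit is added. The headline rate may be less favourable than the placement rate. Counting missing HSGs as not confirmed is conservative: with 8 of 80 missing and 65 of the other 72 occluded (assumed), it gives 65/80 = 81.25%, against 65/72 = 90.3% among women with an HSG. The supportive analysis makes that visible.

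### The complication rate is a stated aim, but the SAP defines no complication outcome and the protocol schedules no assessment that would produce one

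*SAP*

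**What the plan says.** **Aim.** The protocol, under The aims: "The aim of our study was to evaluate the successful and complication rate after occlusion with fibered platinum coils". The same sentence goes on to say that pregnancy after IVF-ET will be observed. The Background section reports severe complications with the Essure device and concludes: "Therefore, another safer device should be investigated".

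**Scheduled procedures.** The protocol's Experimental procedure gives two device checks. The first: "In the third day after the surgery, a vaginal ultrasound will be performed to confirm the position of coil". The second: "3 months later, HSG will be taken out to confirm the occlusion of tubes". IVF-ET and pregnancy follow-up come after these.

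**Outcomes.** SAP section 1 defines the device result: "Successful placement of coils will be judged by the correct placement that confirmed by vaginal ultrasound examination". It then adds: "Implantation rate, first-trimester spontaneous miscarriage rate and on-going pregnancy rate will also be calculated".

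**Analysis.** SAP section 3 describes follow-up as: "The participants who received insertion of fibered coils were followed up and the outcomes were recorded". On summaries it says: "Ratio was applied in the outcomes of miscarriage rate and pregnancy rate".

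**The concern.** An aim becomes a result only if some outcome, collected in a stated way over a stated period, feeds a stated rate. For complications, neither document supplies that chain. There is no list of events, no time window, no denominator and no interval. If the plan is followed to the letter, the report will contain placement and pregnancy results, and half of the device question in the aims will go unanswered.

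The likelier outcome is that a complication figure is added when the paper is written. What counts, until when and over which women would then be chosen after the events are known, from information that nobody was asked to collect systematically. A bare statement that few or no complications occurred would also read as stronger evidence than 80 women can give. This matters because a search for something safer than Essure is a stated reason for testing coils.

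**Working it through.** **Step 1. Match the aims to the outcomes.**

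| Element of the aims | Outcome in the SAP | Scheduled assessment in the protocol |
|---|---|---|
| Success after occlusion | Correct placement on ultrasound | Day-3 ultrasound; 3-month HSG |
| Complications after occlusion | None | None |
| Pregnancy after IVF-ET | Implantation, first-trimester miscarriage, on-going pregnancy | Follow-up after IVF-ET |

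SAP section 1 lists four measurements, none of them a complication. Complications are mentioned in the protocol only in the Background and the aims. The SAP mentions neither complications nor adverse events. The section numbering in the SAP runs 1 to 3 without a gap or redaction mark, so nothing suggests that a safety section was removed.

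**Step 2. Could an existing item serve?** First-trimester miscarriage is listed with the IVF results and can arise only in women who conceive, so it cannot measure procedural harm among all treated women. The day-3 ultrasound could show early displacement or expulsion, but its stated use is to judge position. Neither device check is described as looking for perforation, infection or bleeding.

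**Step 3. What can 80 women show?** The documents give no target rate, power or precision, so the figure of 80 cannot be reproduced; it is taken as given. Assume that insertion is attempted in all 80 and all are followed. The event counts are illustrative. The exact (Clopper-Pearson) two-sided 95% limits for x events are the 0.025 quantile of Beta(x, 80 − x + 1) and the 0.975 quantile of Beta(x + 1, 80 − x). For x = 0 the lower limit is 0 and the upper limit is 1 − 0.025^(1/80) = 0.0451.

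| Events | Rate | Exact 95% limits |
|---|---|---|
| 0/80 | 0% | 0 to 4.5% |
| 1/80 | 1.25% | 0.03% to 6.8% |
| 2/80 | 2.5% | 0.3% to 8.7% |
| 4/80 | 5.0% | 1.4% to 12.3% |

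The chance of at least one event is 1 − (1 − p)^80, which is 55%, 80% and 98% for true rates p of 1%, 2% and 5%. At a true rate of 1%, zero events would therefore be seen about 45% of the time (1 − 0.552 = 0.448).

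**Step 4. Which way would leaving out failed insertions push the rate?** Let f be the fraction of attempts that fail and m the complication risk after a failed attempt relative to a completed one. Then

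rate among inserted women / rate among all attempts = 1 / ((1 − f) + f·m).

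The documents give neither f nor m. Taking f = 0.20 purely as an assumption:

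- m = 4: 1/(0.8 + 0.8) = 0.63
- m = 1: 1/(0.8 + 0.2) = 1.00
- m = 0.5: 1/(0.8 + 0.1) = 1.11
- m = 0: 1/0.8 = 1.25

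A difficult attempt may carry more procedural harm (m above 1). A woman left without a coil has nothing to migrate or be expelled (m below 1). The direction cannot be settled from the documents, and with f = 0 the question disappears.

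**The case against.** The best defence is that these are short documents and that the general statement in SAP section 3 about recording outcomes was meant to include complications. That may be the intention. But the sentence names no event, window or denominator, so no rate can be derived from it.

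Several other counter-arguments stand, and they limit the point:

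- A reader might infer from the sentence on ratios in SAP section 3 that complications were deliberately left out of the analysis. That list is not exhaustive: placement and implantation are missing from it too, although SAP section 1 covers both. The weight rests on SAP section 1 and on the procedures.
- A reader might infer that women with a failed insertion are excluded and that the complication rate will therefore look too low. SAP section 3 says that women who received coils were followed; it does not say that only they were. The protocol times the ultrasound from surgery without limiting it to successful insertions. Exclusion is one reading, and step 4 shows that the bias could go either way.
- A reader might infer that safety is the whole case for coils. The Background also cites reflux after fluid extraction, reduced ovarian response after salpingectomy, and the risk of laparoscopy in women with severe adhesions. The research problem and the hypothesis do not mention complications. Being safer is the argument against Essure in particular.
- A reader might try to show how far the reported rate could swing with the unit or time window chosen. The documents give no event counts, failure rate or share of bilateral cases, so any such figure would be invented.
- The day-3 ultrasound already captures one kind of device problem, so the gap is not total.

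**Conclusion.** The point holds as an omission. The complication rate stands beside success in the aims, yet no outcome in SAP section 1 and no scheduled procedure in the protocol is set up to measure it. The plan as written does not deliver that aim, apart from what the position ultrasound happens to reveal. This conclusion rests on the text alone and needs no numerical assumption.

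Two qualifications go with it. Missed harm at failed attempts is a possibility that the SAP leaves open, with no known direction of bias. The limits for 80 women describe the precision of a complication rate once it is defined, assuming that all 80 have an attempt and are followed; they do not measure an effect of the omission. They do show why an interval is needed: even an event-free series would leave rates up to 4.5% open. The documents do not support the stronger claim that the trial will understate complications.

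**What to change.** **SAP section 1.** Add a complication rate: the number of women with at least one device- or procedure-related complication from the start of hysteroscopy to the 3-month HSG, divided by all women in whom insertion was attempted, with an exact 95% confidence interval and counts by type. A starting list for the sponsor to confirm: perforation, pelvic infection, bleeding needing treatment, coil expulsion or migration, reaction to nickel or contrast, and any unplanned procedure or admission. A tube that is not occluded, or a failed IVF cycle, is an efficacy result and is not counted.

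**Overlap rule.** State that an expulsion or migration seen on day 3 counts both as a placement failure and as a complication, and is reported as such. Without this rule the same event could be moved from one result to the other.

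**SAP section 3.** Name the complication rate among the outcomes summarised, and state that women with a failed insertion are followed for complications.

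**Protocol, Experimental procedure.** Record presence or absence of each listed event at the day-3 and 3-month visits, with a contact at the same times for women whose insertion failed. List complications arising later, during IVF follow-up, separately.

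**Cost.** A paragraph and a small wording change in the SAP, a sentence in the protocol, a short checklist at two visits already planned, and a few extra contacts for women with failed insertion. Sample size, treatment and enrolment do not change.

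### SAP 3 ties follow-up to women who received coils and SAP 1 gives no denominator, so complete insertion failures would, read literally, be missing from the pregnancy outcomes and may be left out of the success rate

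*SAP*

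**What the plan says.** SAP 3 (Statistical methods) states: "The participants who received insertion of fibered coils were followed up and the outcomes were recorded". The same section handles the clinical outcomes in one line: "Ratio was applied in the outcomes of miscarriage rate and pregnancy rate". No numerator or denominator is given.

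SAP 1 (Measurements used) defines success: "Successful placement of coils will be judged by the correct placement that confirmed by vaginal ultrasound examination". It then lists implantation, miscarriage and on-going pregnancy, again without denominators. SAP 2 reads: "As a single-arm trial, 80 females will be recruited in our study". That figure counts women recruited, not women with a coil in place.

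In the Protocol, the research problem is to "evaluate the success rate of proximal tubal occlusion with coil devices in women with hydrosalpinx". Under Experimental procedure, on the third day after surgery, "a vaginal ultrasound will be performed to confirm the position of coil". The same paragraph schedules an HSG at 3 months to check occlusion. It then says that IVF-ET follows treatment and that pregnancy among the patients is assessed at follow-up.

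Neither document defines an analysis set or says how a failed or abandoned insertion is handled.

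**The concern.** The trial has one arm, so its rates are read on their own. Being unable to place the coil is one of the ways in which a placement procedure fails, and a success rate that leaves such cases out answers a narrower question than the one in the Protocol. It matters to these women in particular because of inclusion criterion 2: "Laparoscopic surgery was considered to be contraindicated because of suspected extensive pelvic adhesions". Whether a coil can be placed at all is part of what they need to know.

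For pregnancy, the direction of any bias is conditional. The Protocol's background says: "Many studies have proposed that hydrosalpinx fluid may decrease the pregnancy rate following IVF-ET". A woman whose insertion failed may reach IVF-ET with the hydrosalpinx untreated, or may not reach it. If such women conceive less often, a rate among women with coils overstates what a woman offered the procedure can expect. If they conceive equally often, the pregnancy rate is not biased.

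The two outcomes also differ in whether the loss can be repaired. Placement success per attempt can be rebuilt once the number attempted is reported. A pregnancy outcome that was never recorded cannot.

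**Working it through.** **The plan's own figure.** The only relevant number is 80 women (SAP 2). It comes with no target rate, power or precision, so it can be neither reproduced nor refuted. It is not in dispute here.

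**Reading the text.** Take a woman in whom insertion was attempted and no coil was placed.

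- SAP 3: she did not receive coils, so on the literal reading she is not among those followed.
- SAP 1: she has no correct placement on ultrasound. She is not a success. With no denominator stated, she may be scored as a failure or left out.
- Protocol, Experimental procedure: pregnancy is assessed in the patients after treatment. This might include her, or treatment might mean a completed insertion.

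**Inputs for the size.** All are assumptions except the 80: all 80 women have insertion attempted; k = 0 to 16 complete failures (0-20%); m = 0 to 4 coils misplaced on ultrasound; on-going pregnancy 40% in women with coils; p = 0 to 20% in women with complete failure.

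**Placement success.** Among women with coils: (80 − k − m)/(80 − k). Per woman attempted: (80 − k − m)/80. The gap equals the received-coil rate times k/80.

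| k | m | With coils | Per attempt | Gap (points) |
|---|---|---|---|---|
| 0 | any | same | same | 0 |
| 4 | 0 | 76/76 = 100.0% | 76/80 = 95.0% | 5.0 |
| 4 | 4 | 72/76 = 94.7% | 72/80 = 90.0% | 4.7 |
| 8 | 0 | 72/72 = 100.0% | 72/80 = 90.0% | 10.0 |
| 8 | 2 | 70/72 = 97.2% | 70/80 = 87.5% | 9.7 |
| 8 | 4 | 68/72 = 94.4% | 68/80 = 85.0% | 9.4 |
| 16 | 0 | 64/64 = 100.0% | 64/80 = 80.0% | 20.0 |
| 16 | 4 | 60/64 = 93.8% | 60/80 = 75.0% | 18.8 |

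For k = 8 and m = 2, the exact (Clopper-Pearson) 95% intervals are 90.3-99.7% with coils and 78.2-93.8% per attempt.

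**On-going pregnancy.** Per woman attempted: [(80 − k) × 0.40 + k × p]/80. The gap is therefore k × (0.40 − p)/80.

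| k | Gap if p = 20% | Gap if p = 0 |
|---|---|---|
| 4 | 1 point | 2 points |
| 8 | 2 points | 4 points |
| 16 | 4 points | 8 points |

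If p = 40%, the gap is 0 for every k. In whole numbers with k = 8: 29/72 = 40.3% (28.9-52.5) with coils, against 30/80 = 37.5% (26.9-49.0) per attempt if 1 of the 8 conceives. The difference is small beside either interval.

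**The case against.** A reader might infer that the plan has a rule excluding failed insertions from both rates. The documents do not support that, for four reasons.

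- No denominator is written for success or pregnancy. A woman without a coil has no confirmed correct placement, so SAP 1 can be read to make her a failure, and 80 recruited women would fit the text as a denominator.
- The SAP 3 sentence does not say that nobody else is followed. In a single-arm trial that performs the procedure on its eligible subjects, it may simply describe the treated cohort.
- SAP 3 is not the only text on whose outcomes are assessed. The Protocol refers to pregnancy in the patients after treatment, without requiring a coil in place.
- Bilateral disease is eligible. A woman with one coil placed and one tube failed did receive a coil, stays in follow-up and has a scan to score. Only complete failures can drop out.

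Two further points are fair. The larger effect, on success, rests on the more contestable reading and can be undone by reporting the number attempted. The better-supported effect, on pregnancy, is small. Also, the Protocol's aim speaks of occlusion, which it checks by HSG; it bears here on which women are meant, not on how placement is defined.

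What stands is that the SAP's follow-up sentence, taken literally, leaves out complete failures, and nothing elsewhere brings them back in. If SAP 1 allows two denominators, the choice between them could be made after the data are seen.

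**Conclusion.** The point holds in a conditional form. Followed literally, SAP 3 leaves the pregnancy outcomes of women with complete insertion failure unrecorded, and the missing denominator in SAP 1 means they may also be absent from the success rate. It goes no further than that: the documents do not establish that these women are excluded from the success rate, nor that the success rate would be beyond repair.

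With 0 to 16 complete failures among 80 attempted, the overstatement is 0 to 20 points for success and, at 40% pregnancy with coils and 0-20% without, 0 to 8 points for pregnancy. It is nil for both if no insertion fails, and nil for pregnancy if the failed group conceives equally often. Nothing in the documents shows how common failure is. The plan should be changed because the change is cheap and removes a selection made on the result of the procedure. Confidence is medium.

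**What to change.** - **SAP 3:** replace the follow-up sentence with: *All women in whom coil insertion was attempted are followed up and their outcomes recorded, whether or not a coil was placed.*
- **SAP 1, placement:** add: *Placement success is the number of women with a coil correctly placed in every target tube on the day-3 ultrasound, divided by all women in whom insertion was attempted; a failed insertion counts as a failure.* This also settles how a bilateral case with one failed tube is scored.
- **SAP 1, pregnancy:** add that on-going pregnancy is reported per woman attempted. Rates among women who received coils may be kept as labelled secondary results.

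Care after a failed insertion stays with the clinicians and is recorded, not prescribed.

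No extra procedure is needed. The added work is following the women with failed insertion by records or contact: 4 to 16 women if 5-20% of 80 fail (assumed). Some may have other treatment before transfer, so their pregnancies should be listed separately as well as counted. The reported success rate will look lower if any insertion fails.

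### The SAP's only named test is a chi-square on age and number of IVF-ET cycles, both numeric and without stated categories; age should stay numeric and the cycle count needs a definition

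*SAP*

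**What the plan says.** SAP item 3 (Statistical methods) sets the significance rule, "using two-sided test, and a p value < 0.05 was considered statistically significant", and then names one test: "Chi-square test will be applied to evaluate the basic data of the participants including age and IVF-ET cycles". It gives no categories for either variable, no grouping variable and no outcome for this test. For the clinical outcomes it says only "Ratio was applied in the outcomes of miscarriage rate and pregnancy rate".

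The design has one group: "As a single-arm trial, 80 females will be recruited in our study" (SAP item 2). Age appears in the Protocol as a range without bands, "80 females between 20-45 years old" (section 2, Subjects). On IVF-ET, the Protocol says "After the treatment, IVF-ET will be applied and then the patients' pregnancy rate will be assessed in the following-up" (section 2, Experimental procedure). Neither document gives a number of cycles, a cap, a stopping rule or a length of follow-up.

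**The concern.** There are two separate issues.

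**Age.** A chi-square test works on counts in categories, so it forces a numeric variable into groups. The SAP states no cut-points, which leaves them open to being chosen after the data are seen. Even with a cut fixed in advance, grouping discards information the trial already holds, and the result depends on where the cut falls.

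**IVF-ET cycles.** The SAP lists these with age as participant characteristics, which suggests a history taken at entry. The only IVF-ET that the Protocol describes for participants comes after the coil. The two readings differ in kind. Cycles before the coil are a baseline count. Cycles after it are part of follow-up, and if a woman stops once pregnant, her count is partly determined by her outcome. Testing such a count against pregnancy would be circular.

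At stake is the one inferential analysis named in the SAP. An age relation could be missed, or a cycle relation misread.

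**Working it through.** **The plan's own figure.** The only figure is 80 women in a single arm. No expected rate, effect size, power or precision target is given, so it cannot be reproduced. This point does not dispute it.

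**Inputs from the documents.** n = 80; two-sided 5% level; ages 20-45.

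**Inputs assumed.** Everything else below, including that age or cycles are compared between pregnant and non-pregnant women.

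**1. Age**

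Model: age normal with mean 32 and SD 5, clipped to 20-45; log-odds of pregnancy = log(0.4/0.6) + b × (age − 32), with b = -0.08, -0.12 or -0.15 per year.

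Meaning of the middle slope: the odds ratio per year is exp(-0.12) = 0.89. The odds at 32 are 0.4/0.6 = 0.667. At 37 they are 0.667 × exp(-0.6) = 0.366, a probability of 0.366/1.366 = 27%. At 27 they are 0.667 × exp(0.6) = 1.215, a probability of 1.215/2.215 = 55%.

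Simulated power, comparing pregnant with non-pregnant women:

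| Analysis | b = -0.08 | b = -0.12 | b = -0.15 |
|---|---|---|---|
| t-test on years | 39% | 71% | 86% |
| chi-square, median split | 27% | 52% | 70% |
| chi-square, cut at 35 | 25% | 44% | 60% |
| chi-square, cut at 38 | 14% | 26% | 36% |

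Repeat runs differ by up to about 3 percentage points; the ordering does not change.

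A separate simulation used 30-40% pregnant at the mean age and log-odds of -0.5 to -0.7 per SD. It gave 51-81% for the t-test, 34-63% for a median split, 27-54% for a cut at 35, 25-52% for five bands and 6-14% for single years of age used as categories. With no age effect, the t-test, the two-group splits and the five bands rejected in 4-5% of runs. With a cut fixed beforehand, the cost is therefore lost power, not false positives.

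**2. Cycles, if counted before the coil**

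With prior cycles unrelated to pregnancy, the chi-square rejected in 4.9% of runs. There is no artefact.

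**3. Cycles, if counted after the coil, stopped at pregnancy and tested against pregnancy**

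Assume a constant 35% chance per cycle, at most 3 cycles, and a fraction d leaving after each failed cycle. There is then no true effect of cycle number. Among women whose last cycle is the first or second, the share pregnant is 0.35 / (0.35 + 0.65 × d). Among those who reach the third it is 35%.

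| d | Share pregnant, last cycle 1 or 2 | Share pregnant, last cycle 3 | Chi-square rejects |
|---|---|---|---|
| 0% | 0.35/0.35 = 100% | 35% | 100% |
| 20% | 0.35/0.48 = 73% | 35% | about 80% |
| 40% | 0.35/0.61 = 57% | 35% | 24% |
| 60% | 0.35/0.74 = 47% | 35% | about 5-6% |

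Over a wider grid (20-40% per cycle, at most 2 to 4 cycles) the rejection rate was 100% with nobody leaving, 47-94% with 20% leaving, 4-30% with 50% and 2-9% with 70%.

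**4. The same post-coil cycles compared between two baseline groups with equal chances of pregnancy**

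Rejection was about 4-6%, close to nominal. The artefact comes from grouping by pregnancy, not from the cycle count alone.

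**The case against.** The strongest objection concerns cycles. A reader might infer that the SAP prescribes a circular test, with post-coil cycles that end at pregnancy set against pregnancy and a false-positive rate near 100%. The documents do not support that, for three reasons.

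- Listing cycles beside age as participants' basic data can equally mean earlier cycles. The Protocol's sentence on timing describes when study IVF-ET happens; it does not define the SAP variable.
- No cap, repeat-cycle plan or stopping at pregnancy is written. If each woman has one study cycle, the post-coil count is constant and there is nothing to test.
- The SAP names no pregnancy grouping for this test and assigns pregnancy and miscarriage to a ratio. Other groupings are possible. The Protocol itself mentions unilateral and bilateral disease, and a baseline split of that kind with equal chances of pregnancy keeps the error rate near 5%.

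This objection stands. The cycle issue is a conditional risk that depends on how the missing comparison is filled in.

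On age, it is fair to say that the power figures also presume a comparison with pregnancy, rest on an assumed linear effect on the log-odds scale, and shrink in absolute terms if the effect is weak or the split is at the median. That limits the size of the loss, not its direction: the t-test had more power in every setting with an age effect.

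It is also true that the trial's aims are success, complication and pregnancy rates, and none of these depends on the chi-square. That keeps the severity low.

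**Conclusion.** The point holds for age. The only named test does not suit a numeric variable, its categories are unstated, and a standard numeric analysis would use the same data better. Under the assumed effects the t-test has 39-86% power, against 27-70%, 25-60% and 14-36% for the three chi-square splits. These figures assume that age is compared between pregnant and non-pregnant women, which the SAP does not say.

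For cycles, what is established is an undefined variable. Circularity needs three unwritten conditions together: post-coil counting, stopping at pregnancy, and a test against pregnancy. If all three hold, the false-positive rate runs from about 5% to 100%, depending mainly on how many women leave after a failed cycle. If the count is of earlier cycles, the problem does not arise.

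The point is minor to moderate. The main rates stand whatever is done here.

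**What to change.** Replace the chi-square sentence in SAP item 3 with text such as:

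> Age is summarised in years (mean, SD, range) and kept numeric. Any relation of age to on-going pregnancy is estimated by logistic regression on age in years. IVF-ET cycles before the coil are a baseline count, recorded in the history. IVF-ET cycles after the coil, if more than one, are not tested against pregnancy; they are reported as the number of women starting each cycle and the number pregnant in each. Chi-square or Fisher tests are used only for categorical variables, and the groups compared are named.

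This text works under either meaning of the cycle count.

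The cost is a few sentences in the SAP and, if women have more than one cycle, one small table. One history item may need adding: the Protocol (section 2, Design) mentions collecting epidemiologic data but does not say that earlier IVF-ET cycles are among them. The logistic model assumes a smooth age effect, which is a small price compared with an unstated cut-point.
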